#### 5.1 Assessment of Potential Risks and Benefits

Extemporaneous combination of ACE-i and BBs are often prescribed to control BP without major reported risks. In many cases, combination therapy improves rates of BP control and requires less time to achieve target BP with equivalent or better tolerability than higher-dose monotherapy. Patients with comorbidities may benefit from the effects of different antihypertensive medications classes. Approximately, 70% of patients with hypertension require 2 or more agents to achieve their target BP.7 In a meta-analysis published in 2010, FDCs of

Identification Number: FORM-000050125

Previous Doc Number: CTWI10A

Version Number: 1.0, CURRENT

### **Protocol Template**

Sponsor: Menarini Pharmaceutical Study Code: MEIN/19/ZoNe-HYP/001

Protocol Version\_1 of 16/07/2020

antihypertensive agents not only improved compliance by 21%, but also allowed for a 50% increase in persistence with therapy. Beyond improving compliance, combination therapy in the setting of hypertension management allows for decreased BP variability. Variability in SBP and DBP is associated with an increased risk of myocardial infarction and stroke.

Using combination therapy could also drive a potential economic advantage, including reduced need to switch medications and long-term improvement in control of BP.7

### 6. TRIAL OBJECTIVES AND ENDPOINTS

OBJECTIVES	ENDPOINTS	JUSTIFICATION FOR	
		ENDPOINTS	
PRIMARY			
To assess the antihypertensive	Change in mean sitting DBP between	The association between	
effect of the extemporaneous	Week 0 (Visit 2) and Week 8 (Visit 3)	elevated DBP and increased	
combination of NEB 5 mg and ZOF		mortality risk has been	
30 mg in lowering sitting DBP after		reported several times in	
8 weeks of treatment, in patients		literature. 	
with uncontrolled BP who were			
previously treated with NEB or ZOF			
monotherapies for at least 4 weeks			
SECONDARY			
To assess the antihypertensive	Change in mean sitting SBP	Change in SBP after	
effect of the extemporaneous	between Week 0 (Visit 2) and	8 weeks of treatment will show the added efficacy of	
combination of NEB 5 mg and	Week 8 (Visit 3)	the extemporaneous	
ZOF 30 mg in lowering sitting		combination	
SBP after 8 weeks of treatment			
in patients with uncontrolled BP			
after at least 4 weeks of			
treatment with NEB or ZOF			
monotherapies			
To evaluate the total number	Total number and proportion	The proportion of patients	
and percentage of patients who	. '	at target is a very	

Identification Number: FORM-000050125

Previous Doc Number:
CTWI10A

Version Number: 1.0, CURRENT

#### **Protocol Template**

Sponsor: Menarini Pharmaceutical Study Code: MEIN/19/ZoNe-HYP/001

Protocol Version 1 of 16/07/2020

achieved the BP goal (sitting BP ≤130/80 mmHg) at Visit 2 and Visit 3

 To assess compliance to the monotherapy and extemporaneous combination (actual doses taken versus doses to be taken)

 To evaluate the safety and tolerability of the ZOF and NEB monotherapies, and the extemporaneous combination of NEB 5 mg and ZOF 30 mg after

8 weeks of treatment

- of patients achieving the BP goal (sitting BP ≤130/80 mmHg) at Week 0 (Visit 2) and Week 8 (Visit 3)
- Adherence to treatment will be measured through treatment compliance which is 100 × (actual doses taken versus planned doses to be taken) from Visit 1 to Visit 2 for the monotherapies, and from Visit 2 to Visit 3 for the extemporaneous combination
- Safety and tolerability of the NEB and ZOF monotherapies, as well as extemporaneous combination between NEB 5 mg and ZOF 30 mg will be measured by AEs, SAEs, AEOSI, vital signs, physical examination, ECG, and concomitant medications at Week 0 (Visit 2) and Week 8 (Visit 3)

important clinical indicator of therapeutic success

Monitoring compliance is extremely important to better understand the efficacy of the extemporaneous combination

Incidence of ADRs, AEs, SAEs, vital signs, physical examination, ECG, and concomitant medications needs to be studied to address safety and tolerability of the extemporaneous combination

#### **EXPLORATORY**

- To assess the antihypertensive efficacy at different time points in patients who (1) received NEB or ZOF monotherapies before the run-in period,
- Change in mean sitting SBP and DBP between Visit 1 and Visit 2:
   (a) in the group of patients who were ZOF 30 mg and NEB 5 mg at Visit 1 and continued on the

Evaluation of the antihypertensive efficacy of monotherapies and combination therapy in patients with different CV risk

Identification Number: FORM-000050125

Previous Doc Number:
CTWI10A

Version Number: 1.0, CURRENT

#### **Protocol Template**

Sponsor: Menarini Pharmaceutical Study Code: MEIN/19/ZoNe-HYP/001

Protocol Version\_1 of 16/07/2020

factors

- (2) received any other ACE-i or BB monotherapies before the run-in period.
- same treatment until Visit 2 and (b) in the group of patients who switched to ZOF 30 mg or NEB 5 mg from any other ACE-i or BB at Visit 1 until Visit 2
- Change in mean sitting SBP and DBP between Visit 1 and Visit 3:

   (a) in the group of patients who were on ZOF 30 mg and NEB 5 mg at Visit 1 and continued the same and (b) in the group of patients who switched to ZOF 30 mg or NEB 5 mg from any other ACE-i or BB at Visit 1 until
- Number and proportion of patients achieving the BP goal (sitting BP ≤130/80 mmHg) at Visit 2 and Visit 3 evaluated in patients: (a) who were on ZOF 30 mg and NEB 5 mg at Visit 1 or (b) who switched to ZOF 30 mg or NEB 5 mg from any other ACE-i and BB at Visit 1
- Number and proportion of patients, divided in subgroups based on the hypertension grade, the presence or absence of diabetes, the presence or absence of hypercholesterolemia achieving the BP goal (sitting BP ≤130/80 mmHg) at Visit 2 and

 To assess the antihypertensive effect on patients, based on their hypertension grade, presence or absence of hypercholesterolemia, presence or absence of diabetes at Visit 2 and Visit 3

Identification Number: FORM-000050125

Previous Doc Number: CTWI10A

Version Number: 1.0, CURRENT

#### **Protocol Template**

Sponsor: Menarini Pharmaceutical Study Code: MEIN/19/ZoNe-HYP/001

Protocol Version\_1 of 16/07/2020

Visit 3

ACE-i: Angiotensin converting enzyme-inhibitor; ADR: adverse drug reaction; AE: Adverse event; AEOSI: Adverse event of special interest; BB: beta blocker; BP: blood pressure; CV: Cardiovascular; DBP: diastolic blood pressure; ECG: Electrocardiogram; NEB: Nebivolol; SAE: serious adverse event; SBP: systolic blood pressure; ZOF: Zofenopril calcium

#### 7. STUDY DESIGN

This is a phase IV, open-label, multicenter, multinational, interventional study to assess the effectiveness and safety of the extemporaneous combination of NEB and ZOF in grade 1 to 2 hypertensive patients versus each monotherapy (NEB or ZOF).

The study will be conducted in approximately 15 sites in the European Union countries. The total study duration is 12 weeks including a run-in period of 4 weeks and an assessment period of 8 weeks.

At Visit 1, after providing informed consent, the eligible grade 1-2 hypertensive patients (with blood pressure [BP] ranging from ≥140/90 mmHg to ≤179/109 mmHg), who were on treatment since at least 1 month, with any ACE-i or BB including ZOF 30 mg and NEB 5 mg will be screened for the eligibility criteria including BP. On the same day, the eligible patients will enter the run-in period of 4 weeks (Week -4 to Week 0). Efforts will be made to achieve 1:1 ratio in the enrolment of patients receiving any ACE-i or BB. The eligibility for grade 1-2 hypertension will be based upon the European Society of Cardiology/European Society of Hypertension (ESC/ESH) guidelines 2018, and the BP criteria is defined as mean sitting SBP ≥140 mmHg and ≤179 mmHg and/or mean sitting DBP ≥90 mmHg and ≤109 mmHg.

During the run-in period of 4 weeks (Week -4 to Week 0):

 Patients on ZOF 30 mg or NEB 5 mg will continue the same therapy. Patients on any other ACE-i will be assigned to monotherapy with ZOF 30 mg and the patients on any other BB will be assigned to monotherapy with NEB 5 mg, respectively.

Patients with controlled BP (sitting SBP/DBP ≤130/80 mmHg), at Week 0 (Visit 2), patients with uncontrolled BP (sitting SBP/DBP >130/80 mmHg) whose adherence to the treatment is not included from 80% to 120% or patients who cannot tolerate one of the monotherapies will not proceed further into the study.

Identification Number: FORM-000050125

Previous Doc Number:
CTWI10A

Version Number: 1.0, CURRENT

#### **Protocol Template**

Sponsor: Menarini Pharmaceutical Study Code: MEIN/19/ZoNe-HYP/001

Protocol Version 1 of 16/07/2020

After the run-in period, the patients will be treated with the extemporaneous combination of NEB 5 mg and ZOF 30 mg for 8 weeks (assessment period), ie, from Week 0 (Visit 2) till Week 8 (Visit 3).

To correctly evaluate the additional effect of the combination therapy, the number of patients with uncontrolled BP on NEB or ZOF monotherapy needs to be balanced at Visit 2. In order to maintain a 1:1 ratio during the assessment period, a cap of 110 patients for each arm (ie, NEB and ZOF) will be included at Visit 2 in order to maintain a balanced number of uncontrolled patients entering the assessment period for each drug. The evaluation will be done every 50 patients. If the rate of entrance in the assessment period for one of the 2 tested drugs will deviate more than 5%, a corrective measure will be initiated: according to the enrolment site statistics, one or more sites will be informed to enrol a greater number of patients being treated with the least represented drug in the assessment period. A total number of 290 patients will be screened considering 25% of drop-out rate, to obtain approximately 216 completed patients at the end of the study.

Blood pressure and heart rate will be measured at all visits using a calibrated, fully automated machine with a cuff that is appropriate to the size of the upper arm. If a fully automated machine is not available, BP may be measured manually. The same method (either automated or manual) and the same arm (right or left) must be used throughout the study. The patient should be in a seated position with feet touching the floor. Patients should be seated quietly for several minutes in a chair with their backs supported, their feet flat on the ground, and their arms bared and supported at heart level. At each clinic visit, 3 BP measurements will be collected 24 hours (±3 hours) after the last study drug intake and the mean values will be recorded. Each BP measure must be recorded within ±2 mmHg. Patients will be instructed to take study medication at the same time each day except on the days of study visits when study medication will be taken after all visit evaluations have been performed.

The patients will attend an End of Treatment at Visit 3 (Week 8) at the end of assessment period. Safety (AEs, SAEs) will be measured at all visits. In case of any abnormality of clinically relevant safety finding at any of the visits according to the Investigator, the patient will be

Identification Number: FORM-000050125

Previous Doc Number:
CTWI10A

Version Number: 1.0, CURRENT

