### Exploratory endpoint:

- Change in mean sitting SBP and DBP between Visit 1 and Visit 2:
   (a) in the group of patients who were on ZOF 30 mg and NEB 5 mg at Visit 1 and continued on the same treatment until Visit 2 and (b) in the group of patients, who switched to ZOF 30 mg or NEB 5 mg from any other ACE-i or BB at Visit 1 until Visit 2.
- Change in mean sitting SBP and DBP between Visit 1 and Visit 3: (a) in the group of patients who were on ZOF 30 mg and NEB 5 mg at Visit 1 and continued on the same treatment until Visit 2 and (b) in the group of patients who switched to ZOF 30 mg or NEB 5 mg from any other ACE-i or BB at Visit 1 until Visit 2.
- Number and proportion of patients achieving the BP goal (sitting BP ≤130/80 mmHg) at Visit 2 and Visit 3 evaluated in the patients: (a) who were on ZOF 30 mg and NEB 5 mg at Visit 1 or (b) who switched to ZOF 30mg or NEB 5 mg from any other ACE-i and BB at Visit 1
- Number and proportion of patients, divided in subgroups based on the hypertension grade, the presence or absence of diabetes, the presence or absence of hypercholesterolemia achieving the BP goal (sitting BP ≤130/80 mmHg) at Visit 2 and Visit 3

Study Population: Patients characteristics Number of Patients Approximately, 290 male or female Caucasian uncontrolled hypertensive patients between ≥18 and <65 years of age, who are on treatment with ZOF or NEB, or, on any other ACE-i or BBs, for at least 1 month, will be screened for eligibility.

A total drop-out rate of 25% from Visit 1 to Visit 3, has been considered. A

Identification Number: FORM-000050125

Previous Doc Number:
CTWI10A

Version Number: 1.0, CURRENT

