#### 14.2 Determination of Sample Size

Considering a screen failure and a drop-out rate of 25% from Visit 1 and Visit 3, the number of patients to be screened is 290. Two-hundred and sixteen with uncontrolled hypertension, are planned to be included at Screening in the assessment period lasting for 8 weeks. A total sample size of 216 patients is required to achieve 90% power at 5% significance level assuming a difference in mean DBP from baseline to 8 weeks of 4 mmHg and a standard deviation (SD) for this difference of 10 mmHg. The mean change in DBP for null hypothesis is set at 2 mmHg.

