#### 3. STUDY DESIGN

#### 3.1. GENERAL DESCRIPTION

This is a phase IV, open-label, multicenter, multinational study with 2 study periods (a run-in period of 4 weeks and an assessment period of 8 weeks). Grade 1-2 hypertensive patients (blood pressure [BP] ranging from  $\geq$ 140/90 mmHg to  $\leq$ 179/109 mmHg) on treatment with any angiotensin converting enzyme-inhibitors (ACE-i) or beta blockers (BBs) including ZOF 30 mg or NEB 5 mg respectively will be screened for eligibility (Visit 1). On the same day, the eligible patients will enter into a run-in period after Screening, during which:

- Patients on ZOF 30 mg or NEB 5 mg will continue the same therapy for 4 weeks
- Patients on any other ACE-i will be assigned to monotherapy with ZOF 30 mg while patients on any other BB will be assigned to monotherapy with NEB 5 mg, respectively, for 4 weeks.

After the 4 weeks of monotherapy in the run-in period, if BP at Visit 2, remains uncontrolled (sitting SBP/DBP >130/80 mmHg) despite an adherence to the treatments ranging from 80% to 120%, the patients will start treatment (Week 0, Visit 2) with the extemporaneous combination of NEB 5 mg/ZOF 30 mg (NEB/ZOF) and will be assessed for further 8 weeks (assessment period). If the patients, at Visit 2 after the Run-In period, have controlled BP (sitting SBP/DBP ≤130/80 mmHg), and/or do not tolerate the treatment, and/or do not maintain the adherence to the therapy (range from 80% to 120%), these patients will not be continued further in the study. At the end of the assessment period (Visit 3) the antihypertensive effect of the extemporaneous combination of NEB 5 mg and ZOF 30 mg will be evaluated. A total number of 290 patients will be screened considering 25% of drop-out rate, to obtain approximately 216 completed patients at the end of the study.

Document: \\ieedc-vnasc01\BIOSdata\Menarini\NebZof\KZA41200\Biostatistics\Documentation\SAP

[figure not shown]
Author: [name] Version Number: Final V1.0

Version Date: [14Dec2021]

Template No.: CS\_TP\_BS016 Revision 6 Reference: CS\_WI\_BS005

Page 14 of 37

Figure 1: Study Scheme

BP: Blood pressure, NEB: Nebivolol, ZOF: Zofenopril calcium, ACE-i: Angiotensin converting enzyme-inhibitors, BB: Beta blockers

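### 216 serves as both the number entering and the number completing the assessment period, and the 220-patient entry cap leaves room for only 4 losses (1.8%) in eight weeks

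*Protocol*

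**What the plan says.** The number 216 appears in two roles.

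- **As entrants.** Protocol 14.2: "Two-hundred and sixteen with uncontrolled hypertension, are planned to be included at Screening in the assessment period lasting for 8 weeks". The sentence names Screening and the assessment period together, but the number is attached to the eight-week period.
- **As completers.** SAP 3.1 screens 290 patients "to obtain approximately 216 completed patients at the end of the study". The Protocol synopsis and Section 7 say the same.

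Protocol 14.2 also makes it the statistical requirement: "A total sample size of 216 patients is required to achieve 90% power at 5% significance level", for a mean DBP change of 4 mmHg against a null value of 2 mmHg, with SD 10 mmHg.

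Entry at Visit 2 is limited in Protocol Section 7: "a cap of 110 patients for each arm (ie, NEB and ZOF) will be included at Visit 2".

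Attrition is one undivided figure, described in two ways. Protocol 14.2 counts screen failures in it: "Considering a screen failure and a drop-out rate of 25% from Visit 1 and Visit 3, the number of patients to be screened is 290". The synopsis calls it drop-out only: "A total drop-out rate of 25% from Visit 1 to Visit 3, has been considered". Patients also leave at Visit 2 if their BP is controlled. Under Protocol Section 7, so do uncontrolled patients "whose adherence to the treatment is not included from 80% to 120% or patients who cannot tolerate one of the monotherapies will not proceed further".

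SAP 3.3 withdraws the multiple imputation planned in Protocol 14.5.9 and restricts the primary analysis to observed data. SAP 7.3 confirms that nothing is imputed.

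**The concern.** The paired test needs a Week 8 reading, so under the SAP the number that carries the power is the number of patients with an observed Week 8 value. That makes it important whether 216 is counted at Visit 2 or at Visit 3.

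If 216 is the number entering, as 14.2 says, nothing has been added for loss during the eight weeks. If it is the number completing, the entry ceiling of 220 allows almost no loss. Either way, the stated 90% power belongs to a number that the plan's own entry figures deliver only if nearly everyone who starts the combination also supplies a Week 8 reading. Because the 25% is not divided at Visit 2, the reader cannot tell how much loss was expected in that period.

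**Working it through.** **Inputs.** Protocol 14.2: change 4 mmHg, null 2 mmHg, SD 10 mmHg, power 90%, level 5% (sidedness not given), 290 screened, 25% overall loss. Protocol Section 7: 110 per drug at Visit 2. SAP 6.5: two-sided tests. SAP 3.3 and 7.3: observed data only.

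**1. Reproduce 216.** For a paired mean, n = (SD × (z_alpha + z_power) / (4 − 2))².
- One-sided 5%: (10 × (1.645 + 1.282) / 2)² gives 215. The exact noncentral t gives 216, with power 90.1% at 216. The stated figure reproduces.
- Two-sided 5%: (10 × (1.960 + 1.282) / 2)² gives 263. The exact noncentral t gives 265, and power at 216 is 83.3%. The stated figure does not reproduce.

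**2. Reproduce 290.** 216 / (1 − 0.25) = 288, and 290 × 0.75 = 217.5. So 290 is consistent with about 216 patients remaining at Visit 3 after all losses from Visit 1, which is the completer meaning of 216.

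**3. Apply the entry cap.** 2 × 110 = 220 entrants at most. 220 − 216 = 4, and 4 / 220 = 1.8%, or 2 patients per drug.

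**4. Divide the attrition.** From 290 to 216 is 74 losses. From 290 to 220 is 70 losses, and 70 / 290 = 24.1%. Reaching the ceiling at Visit 2 therefore uses 70 of the 74, leaving 4 for the eight weeks.

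**5. Does it matter whether the cap binds?** It limits the total only if more than 220 of 290 reach Visit 2, that is, if loss before Visit 2 is below 24.1%.
- If it binds, 220 enter.
- If it does not, 220 or fewer enter.

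The completer numbers below are therefore maxima in both cases.

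**6. Completers and power.** The documents give no loss rate after Visit 2, so the first column is an assumption. Completers = 220 × (1 − loss). Power is from the noncentral t with the 14.2 inputs.

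| Assumed loss after Visit 2 | Completers from 220 | Power, one-sided 5% | Power, two-sided 5% |
|---|---|---|---|
| 5% | 209 | 89.2% | 82.1% |
| 10% | 198 | 87.7% | 80.0% |
| 15% | 187 | 86.0% | 77.7% |
| For reference: 216 analysed | 216 | 90.1% | 83.3% |

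**7. Entrants needed for 216 completers.** 216 / (1 − loss) is 228, 240 or 255 at 5%, 10% or 15%, all above 220.

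**The case against.** Several points on the other side stand.

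- The text says about 216, so a ceiling of 220 and roughly 216 completers are tight rather than flatly contradictory.
- No eight-week loss rate is given, so a loss above 1.8% is plausible but is an assumption.
- The cap is not the only cause. With heavy loss before Visit 2 it may never limit the total, and the weak point is then the single 25% applied to 290.
- Protocol Section 12 asks early leavers to complete the Visit 3 assessments, so some losses may still yield a reading. How many would count is unclear: SAP 6.4 assigns Week 8 to Days 53–59 only, and SAP 6.3 mentions early-discontinuation data only for listings.
- The power cost is modest. On the basis that reproduces 216, 10% loss takes power from 90.1% to 87.7%. The larger two-sided deficit comes mainly from sidedness (83.3% even with all 216), which is a separate matter.

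A reader might infer two stronger things. One is that the cap blocks the trial from reaching its sample size. The documents do not show this, for the first three reasons above. The other is that qualified run-in patients are turned away for a reason unrelated to the objective. Section 7 ties balance between the drugs at Visit 2 to the evaluation of the combination's added effect, and manages it with checks every 50 patients and redirected enrolment. No text says what happens to a patient who qualifies after a cap is full, so exclusion is an inference.

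None of this settles which meaning of 216 applies or supplies an allowance for loss after Visit 2.

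**Conclusion.** Wrong as written. 216 is used as entrants, as completers and as the number required for 90% power. With entry capped at 220 and only observed Week 8 data analysed, these uses agree only if at most 4 patients (1.8%) are lost after Visit 2; if 216 is the number entering, no loss is allowed for. At an assumed 10% loss, at most 198 are analysed, 18 below the stated number, with 87.7% power one-sided or 80.0% two-sided. These results rest on the 14.2 effect and SD, on the assumed loss rates, and on early leavers' readings not counting as Week 8 values. The finding is that a stated number and its power need correcting. It is not a finding that the trial cannot succeed.

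**What to change.** Keep the cap of 110 per drug and the 290 screened, and make the figures agree:

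1. Define 216 once, as evaluable completers (patients with an observed Week 8 DBP), and correct the 14.2 sentence that gives it as the number entering.
2. Split the 25% into loss before Visit 2 (screen failure, controlled BP, intolerance, adherence out of range) and loss after it. Say everywhere whether screen failures are included.
3. State in 14.2, the synopsis, Section 7 and SAP 3.1 the expected number analysed from 220 entrants and its power at the stated post-Visit 2 loss, naming the sidedness. At 10%, for example, this is 198 analysed, with 87.7% power one-sided or 80.0% two-sided.
4. Reconcile the Visit 2 entry conditions with the cap, so that the protocol covers run-in patients who qualify after a drug's cap is full.

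A cap counted on completers would not work, because completion is known only eight weeks after entry. Raising the cap is a larger change: 240 entrants from 290 screened would require loss before Visit 2 of no more than 50 / 290 = 17.2%.

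The cost is wording in both documents and a slightly less favourable stated number and power.

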#### **Protocol Template**

Sponsor: Menarini Pharmaceutical Study Code: MEIN/19/ZoNe-HYP/001

Protocol Version\_1 of 16/07/2020

contacted over phone within 24 hours ensuring their safety measures. Any patient having an ongoing AE or SAE at the End of Treatment (Visit 3), will be followed for further 2 weeks over phone.

Patients included in the study should follow the diet and lifestyle counselling.

At the End of Treatment Visit patients will be advised to maintain the recommended diet and physical activity/exercise pattern as per local standards of care.

